2.2. Secondary objectives

- Efficacy
 - To assess the incremental vaccine efficacy against clinical malaria of a schedule with a fractional third dose at Month 2 versus a schedule with 3 full doses (primary and secondary case definitions) over 12 months post-Dose 3.
 - To assess the incremental vaccine efficacy against clinical malaria, over 7 and 12 months post-Dose 3, of a schedule with a fractional third dose at Month 7 versus a schedule with a fractional third dose at Month 2.
 - To assess the incremental vaccine efficacy against clinical malaria, over 7 and 12 months post-Dose 3, of a schedule with a fractional third dose at Month 7 versus a schedule with 3 full doses.

- To assess the incremental vaccine efficacy against clinical malaria, over 12 months post-Dose 4, post-Dose 5 and post-Dose 6 of a schedule with a fractional third dose at Month 2 and yearly fractional doses versus a schedule with full doses at Month 0, Month 1, Month 2 and yearly full doses.
- To assess the incremental vaccine efficacy against clinical malaria, over 12 months post-Dose 4, of a schedule with a fractional third dose at Month 7 versus a standard schedule with 4 full doses at 0,1,2,20 months.
- To assess the vaccine efficacy and impact of each RTS,S/AS01_E schedule over the entire study period by measuring the efficacy against clinical malaria at Months 14, 20, 26, 32, 38 and 50.
- To assess the prevalence of *P. falciparum* infections of each RTS,S/AS01_E schedule at cross-sectional visits (monthly from Month 0-20 and every three months thereafter till study end).
- To assess the vaccine efficacy against incident *P. falciparum* infections defined by positive blood slide over the entire study period.
- **Immunogenicity: Immune response to the CS and HBs antigens**
 - To describe the antibody response to the anti-circumsporozoite protein of *P. falciparum* (anti-CS) for each schedule.
 - To describe the antibody response to the hepatitis B surface antigen (anti-HBs) for each schedule.
- **Safety and reactogenicity**
 - To assess the safety of RTS,S/AS01_E for each schedule in terms of serious adverse events (SAEs), unsolicited adverse events (AEs) and AEs of specific interest.
 - To assess the reactogenicity of RTS,S/AS01_E in terms of solicited local and general AEs.
 - To assess the safety of RTS,S/AS01_E in terms of biochemistry (alanine aminotransferase [ALT], creatinine) and hematology (hemoglobin, white blood cells [WBC], platelets) parameters.

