- All AEs and SAEs leading to withdrawal from further vaccination will be reported until study end (Month 50).
- Meningitis and pIMDs are AEs of specific interest to be reported until study end (Month 50). All seizures occurring within 30 days post-vaccination are also AEs of specific interest. Clinical details according to the Brighton collaboration guidelines [Bonhoeffer, 2004] pertaining to seizures occurring within seven days of vaccination will be documented in a specific eCRF screen. All AEs of specific interest are to be reported as SAEs (see Section 9.1.6).
- Reactogenicity data collection will be aimed at characterizing reactions to the fractional doses relative to full doses and reactions to a fourth dose and multiple yearly doses, full or fractional. Post-Dose 1 and post-Dose 2 data will not be collected as these have already been largely characterized in previous studies including Phase III evaluation. Solicited local and general AEs will be collected in the first 50 subjects enrolled in each group (reactogenicity sub-cohort) during four days (day of vaccination and three subsequent days) after Dose 3 of study vaccine (all groups including controls), after Dose 4 (R012-20, R012-14-mD, Fx012-14-mFxD and Fx017-mFxD), after Dose 5 (R012-14-mD, Fx012-14-mFxD and Fx017-mFxD) and after Dose 6 (R012-14-mD and Fx012-14-mFxD). Evidence from Phase III evaluation showed that the significant reactogenicity reactions to RTS,S/AS01E are concentrated in the first 48 hours post-vaccination. On the day of vaccination the evaluation will be carried out by the study physician at the study center. On Days 1, 2 and 3 after vaccination, trained study personnel will visit the children to record solicited AEs on diary cards.
- Unsolicited AEs will be collected during 30 days (day of vaccination and 29 subsequent days) after each dose of study vaccine. Unsolicited AEs will be captured through passive surveillance at inpatient and outpatient facilities and during study visits.
- Biochemistry (ALT, creatinine) and hematology (hemoglobin, WBC, platelets) parameters will be assessed in the first 50 subjects enrolled in each group (reactogenicity sub-cohort) before Dose 3, seven days post-Dose 3 and 30 days post-Dose 3.

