5. STUDY COHORT

5.1. Number of subjects/centers

Approximately 1500 subjects (300 per group) will be enrolled in this study. Refer to Section 11.4 for a detailed description of the criteria used in the estimation of sample size.

In this study the biochemistry and hematology parameters and the reactogenicity will be evaluated in a sub-cohort of subjects. The anti-CS and anti-HBs immune responses will be tested in a subset; see the [glossary of terms](#) for the definitions of subset and sub-cohort.

Table 9 Sub-cohort

Sub-cohort name	Description	Estimated number of subjects
Reactogenicity*	Solicited local and general AEs will be collected in a sub-cohort consisting of the first 50 subjects enrolled in each group. Hematology and biochemistry parameters will be measured in the same sub-cohort.	250 (50 subjects per group, 25 subjects per site)

* Subjects belonging to this sub-cohort will have specific study procedures performed for the assessment of reactogenicity, hematology and biochemistry parameters (refer to [Table 11](#), [Table 12](#) and [Table 13](#)).

Table 10 Subset

Subset name	Description	Estimated number of subjects
Immunogenicity*	Anti-CS and anti-HBs immune responses will be tested in a subset corresponding to the first 50 subjects enrolled in each group.	250 (50 subjects per group, 25 subjects per site)

*In this study, all subjects enrolled will have blood samples taken for assessment of immunogenicity. Not all samples will be used for testing: anti-CS and anti-HBs immune responses will be tested in a subset (i.e. the immunogenicity subset which includes the same subjects as in the reactogenicity sub-cohort) CC1

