11.10. Analysis of safety

The primary analysis will be based on the TVC.

Among the reactogenicity sub-cohort (first 50 subjects enrolled in each group) the percentage of subjects with at least one local AE (solicited and unsolicited), with at least one general AE (solicited and unsolicited) and with any AE during the solicited follow-up period (i.e. four days post-Dose 3, Dose 4, Dose 5 and Dose 6) will be tabulated with exact 95% CI after each vaccine dose and overall. The percentage of doses followed by at least one local AE (solicited and unsolicited), by at least one general AE (solicited and unsolicited) and by any AE will be tabulated for the whole solicited follow-up period (i.e. four days post-Dose 3, Dose 4, Dose 5 and Dose 6), with exact 95% CI. Similar tables will be generated for Grade 3 AEs and AEs considered as causally related to vaccination.

Among the reactogenicity sub-cohort (first 50 subjects enrolled in each group), the percentage of subjects reporting each individual solicited local and general AE during the solicited follow-up period (i.e. four days post-Dose 3, Dose 4, Dose 5 and Dose 6) will be tabulated with exact 95% CI. The percentage of doses followed by each individual solicited local and general AE will be tabulated for each dose and for the whole solicited follow-up period (i.e. four days post-Dose 3, Dose 4, Dose 5 and Dose 6), with exact 95% CI. Similar tables will be generated for Grade 3 AEs, causal events and for fever, temperature in 0.5°C increments.

The verbatim reports of unsolicited symptoms will be reviewed by a physician and the signs and symptoms will be coded according to the MedDRA. The percentage of subjects with at least one report of unsolicited AE classified by the MedDRA preferred term level, occurring within 30 days (day of vaccination and 29 subsequent days) after each dose of study vaccine will be tabulated with exact 95% CI.

The percentage of subjects reporting an SAE (all, fatal, related) occurring within 30 days (day of vaccination and 29 subsequent days) after each dose of study vaccine, classified by the MedDRA preferred term level will be tabulated with exact 95% CI.

The percentage of subjects reporting an SAE (all, fatal, related) from Dose 1 (Day 0) until Month 14, from Day 0 until Month 26 and over the whole study duration (Dose 1 [Day 0] until Month 50), classified by the MedDRA preferred term level, will be tabulated with exact 95% CI.

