7.5. Analysis of safety and reactogenicity

7.5.1. Analysis of safety and reactogenicity planned in the protocol

The primary analysis of safety will be based on the ES. Analyses containing only solicited data will be based on the solicited safety set.

Among the reactogenicity sub-cohort (first 50 subjects enrolled in each group) the percentage of subjects with at least one local AE (solicited and unsolicited), with at least one general AE (solicited and unsolicited) and with any AE during the solicited follow-up period (i.e. four days post-Dose 3, Dose 4, Dose 5 and Dose 6) will be tabulated with exact 95% CI after each vaccine dose and overall. The percentage of doses followed by at least one local AE (solicited and unsolicited), by at least one general AE (solicited and unsolicited) and by any AE will be tabulated for the whole solicited follow-up period (i.e. four days post-Dose 3, Dose 4, Dose 5 and Dose 6), with exact 95% CI. Similar tables will be generated for Grade 3 AEs and AEs considered as causally related to vaccination.

Among the reactogenicity sub-cohort (first 50 subjects enrolled in each group), the percentage of subjects reporting each individual solicited local and general AE during the solicited follow-up period (i.e. four days post-Dose 3, Dose 4, Dose 5 and Dose 6) will be tabulated with exact 95% CI. The percentage of doses followed by each individual solicited local and general AE will be tabulated for each dose and for the whole solicited follow-up period (i.e. four days post-Dose 3, Dose 4, Dose 5 and Dose 6), with exact 95% CI. Similar tables will be generated for Grade 3 AEs, causal events and for fever, temperature in 0.5°C increments.

The verbatim reports of unsolicited symptoms will be reviewed by a physician and the signs and symptoms will be coded according to the MedDRA. The percentage of subjects with at least one report of an unsolicited AE classified by the MedDRA preferred term level, occurring within 30 days (day of vaccination and 29 subsequent days) after each dose of study vaccine will be tabulated with exact 95% CI.

204889 (Malaria-094) Statistical Analysis Plan

The percentage of subjects reporting an SAE (all, fatal, related) occurring within 30 days (day of vaccination and 29 subsequent days) after each dose of study vaccine, classified by the MedDRA preferred term level will be tabulated with exact 95% CI.

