11. ANNEXES

11.1. Business rules for standard data derivations and statistical methods

This section contains GSK Vaccines' standard rules for data display and derivation for clinical and epidemiological studies. These rules will be applied along with those detailed in section 10 (additional study-specific rules)

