11.1.4. Statistical methodology

11.1.4.1. Exact confidence intervals around proportions

The exact CIs around within-group proportions are derived using the method of Clopper and Pearson [Bonhoeffer, 2004; Clopper, 1934].

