11.1.4.2. Standardized asymptotic confidence intervals around differences in proportions

The standardized asymptotic CIs around differences in proportions are derived using the method of Mietinnen and Nurminen [Miettinen, 1985].

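### Reactogenicity is collected to set fractional against full doses, but no between-group estimate is pre-specified and the two identical full-dose arms are not pooled at Dose 3

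*SAP*

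**What the plan says.** **Purpose.** Protocol Section 3, under safety monitoring: "Reactogenicity data collection will be aimed at characterizing reactions to the fractional doses relative to full doses". The same sentence adds reactions to a fourth dose and to repeated yearly doses. The formal objective in Protocol 2.2 is looser and names no comparator: "To assess the reactogenicity of RTS,S/AS01_E in terms of solicited local and general AEs".

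**Population.** Protocol 5.1: "Solicited local and general AEs will be collected in a sub-cohort consisting of the first 50 subjects enrolled in each group". That is 50 per group and 250 in all, from a 1:1:1:1:1 randomisation.

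**Analysis.** SAP 7.5.1 tabulates "the percentage of subjects reporting each individual solicited local and general AE during the solicited follow-up period" with an exact 95% CI. Protocol 11.10 does the same, and adds that the percentage of doses followed by each event "will be tabulated for each dose and for the whole solicited follow-up period". Similar tables are planned for Grade 3 events, causally related events and fever. SAP 11.1.4.1 defines the interval: "The exact CIs around within-group proportions are derived using the method of Clopper and Pearson".

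**Method for differences.** SAP 11.1.4.2: "The standardized asymptotic CIs around differences in proportions are derived using the method of Mietinnen and Nurminen". This sits in an annex introduced as company-wide text: "This section contains GSK Vaccines' standard rules for data display and derivation for clinical and epidemiological studies". No analysis in SAP Section 7 refers to it.

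**The concern.** The stated purpose is relative, so the natural summary is a difference between randomised groups given a fractional or a full dose in the same month. The plan reports each group's percentage and leaves the contrast to the reader. With at most 50 children per group, two separate exact intervals are a blunt way to judge a difference, and an appreciable fall in fever or local reactions after the fractional dose could look inconclusive.

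The full-dose information at Dose 3 is also split over two columns of 50 when it could be one of 100. Efficacy is handled differently: SAP 7.3.1.5 and 7.3.1.6 name the fractional-versus-full contrasts and pool R012-20 with R012-14 up to Month 14.

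At stake is how sharply the trial answers its own question on tolerability. No efficacy conclusion depends on it.

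**Working it through.** **1. Is a between-group estimate specified anywhere?** Protocol 11.10 and SAP 7.5.1, 7.5.2, 8 and 10 contain no risk difference, ratio, test, pooled full-dose column or named contrast for solicited events. SAP 11.1.3.2 (display of differences) and 11.1.4.2 (their CI) are generic annex rules that no Section 7 analysis calls. The table shells are held outside the two documents (SAP 11.2) and could not be checked.

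**2. Which contrasts does the design support?** From Protocol Table 23 and the solicited-event schedule:

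| Dose (month) | Fractional | Full | Sub-cohort sizes at most |
|---|---|---|---|
| 3 (M2) | Fx012-14 | R012-20 + R012-14 | 50 v 100 |
| 4, 5, 6 (M14, M26, M38) | Fx012-14 | R012-14 | 50 v 50 |
| 4 (M20) | Fx017-20 | R012-20 | 50 v 50 |

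Fx017-20 receives Dose 3 at Month 7, when no group receives a full dose, so it has no same-month comparator. The across-dose percentages cannot stand in for these contrasts. Solicited data cover Doses 3-4 in R012-20, 3-6 in R012-14 and Fx012-14, 3-5 in Fx017-20 and Dose 3 only in Control.

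**3. Size of the gain.** The documents give no reactogenicity rates, power or precision, so there is no plan figure to reproduce. Rates below are assumed. For every pair of counts (x1 of n1, x2 of n2), weighted by its binomial probability, two rules are scored:

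- (a) the two Clopper-Pearson 95% CIs do not overlap;
- (b) the score test of zero difference gives |z| > 1.96, where z = (x1/n1 − x2/n2) / √[p(1−p)(1/n1 + 1/n2) × N/(N−1)], p = (x1+x2)/N and N = n1+n2. This corresponds to the Miettinen-Nurminen 95% CI excluding zero.

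| Full v fractional rate | (a) 50 v 50 | (b) 50 v 50 | (b) 50 v 100 |
|---|---|---|---|
| 30% v 10% | 32% | 72% | 83% |
| 40% v 20% | 21% | 60% | 71% |
| 30% v 15% | 11% | 44% | 54% |
| 30% v 30% | 0.3% | 5.0% | 5.1% |

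Pooling alone does not close the gap: under rule (a) with 50 v 100, 30% v 10% is separated with probability 49%.

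**4. Worked example.** Take 10/50 (20%) after a fractional dose and 40/100 (40%) after a full dose. The exact CIs are 10.0-33.7% and 30.3-50.3%, which overlap. For the difference, p = 50/150 = 0.333. The variance is 0.333 × 0.667 × (1/50 + 1/100) × 150/149 = 0.00671, so the SE is 0.0819 and z = −0.20/0.0819 = −2.44. The Miettinen-Nurminen difference is −20 points (95% CI −33.6 to −4.2), which excludes zero.

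**5. What n = 50 can deliver.** For fractional rates of 10-50%, a two-sided 5% comparison has 80% power for differences of about 20-24 points (50 v 100) or 23-28 points (50 v 50). With equal true rates in that range, the half-width of the difference CI is about 10-17 or 12-20 points. This is estimation, not confirmation.

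**The case against.** A reader might infer that the fractional-versus-full comparison is never made. The documents do not support that. Results are tabulated by randomised group and by dose, so Dose 3 in Fx012-14 can be read beside R012-20 and R012-14, and Dose 4 in Fx017-20 beside R012-20. What is missing is a pre-specified estimate of the difference.

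It is equally tempting to say that an objective goes unmet, or that the SAP departs from the protocol. Neither follows. The formal objective only asks for reactogenicity to be assessed, with no comparator or margin. SAP Section 8 makes this endpoint descriptive, and the two documents agree. Nor does the uncalled method in SAP 11.1.4.2 show that an analysis was dropped, since the annex is standard text.

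The strongest point against the size is that the documents prescribe no overlap rule. Anyone with the counts and denominators can compute a difference later, so no information is lost. This stands: the percentages in the working describe a poor reading habit, at assumed rates.

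The remedy also has limits:

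- Assessment is open-label, and several solicited events (pain, irritability, drowsiness, appetite) are partly subjective. A CI does not cover ascertainment bias.
- At Doses 4-6 only children still being vaccinated and with solicited data contribute. 50 v 50 is a ceiling there, and the contrast is no longer fully protected by randomisation.
- Seven solicited events × two grades (any, Grade 3) × five contrasts = 70 intervals. If every true difference were zero, about 70 × 0.05 = 3.5 would be expected to exclude zero.
- For rarer events the yield is lower. At an assumed 15% v 5%, rule (b) gives 38.5% (50 v 50) and 45% (50 v 100).

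None of this argues against stating the contrasts in advance. It argues for labelling them plainly.

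**Conclusion.** The point holds in a limited form. Data whose stated purpose is relative are to be summarised only within groups, and two arms that are identical at Dose 3 are left unpooled. A better summary is available from the same data.

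At an assumed 30% v 10%, the probability of a clear separation rises from 32% by overlap of separate CIs to 72% (50 v 50) or 83% (50 v 100) with a CI for the difference. These figures depend on the assumed rates, on full sub-cohorts, and on readers otherwise relying on overlap. The table shells could already hold a difference column. If so, only the SAP text needs aligning.

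This is a modest improvement to a descriptive secondary safety objective. It is worth making because it is cheap. The primary analysis and the hierarchically tested secondary comparison are untouched.

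**What to change.** In SAP 7.5.1, for each solicited event (any grade and Grade 3, including fever), add the fractional-minus-full risk difference with the Miettinen-Nurminen 95% CI of SAP 11.1.4.2, for:

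- Fx012-14 v pooled R012-20 + R012-14 after Dose 3;
- Fx012-14 v R012-14 after each of Doses 4, 5 and 6;
- Fx017-20 v R012-20 after Dose 4.

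Report Fx017-20 Dose 3 (Month 7) separately, without a full-dose contrast. State that all intervals are descriptive with no multiplicity claim, that assessment is open-label, and that the contrasts at Doses 4-6 include only children still vaccinated who have solicited data. Show the denominators.

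The cost is a short paragraph in the SAP, an entry in SAP Section 10 and extra columns in existing tables. No new data, visits or alpha are needed. The price is up to 70 further descriptive intervals, a few of which would exclude zero by chance.

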 - The occurrence of solicited local and general AEs in the first 50 subjects enrolled in each group within four days (day of vaccination and three subsequent days) after Dose 3 of study vaccine (all groups including controls), after Dose 4 (groups R012-20, R012-14-mD, Fx012-14-mFxD and Fx017-mFxD), after Dose 5 (groups R012-14-mD, Fx012-14-mFxD and Fx017-mFxD) and after Dose 6 (groups R012-14-mD and Fx012-14-mFxD).

11.3. **Tertiary endpoints**

- **Immunogenicity**
 - Anti-CS antibody avidity at specified timepoints.

11.4. **Determination of sample size**

For the primary endpoint, demonstrating incremental vaccine efficacy against clinical malaria of a fractional dose schedule over the standard schedule, the study has at least 90% power to show a significant incremental vaccine efficacy (lower limit of 95% CI above 0), assuming 250 evaluable subjects per group and an incidence of at least 0.5 episodes/person year at risk (pyr) in the Control group, 0.29 episodes/pyr in the standard schedule groups and 0.16 episodes/pyr in the fractional dose schedule. This corresponds to an incremental efficacy (1-Hazard Rate) of 50% of the fractional dose schedule over the standard schedule. The primary endpoint compares the R012-20+R012-14-mD groups versus the Fx012-14-mFxD group (2:1). For secondary endpoints evaluating efficacy against *P. falciparum* infections, it is anticipated that incidence of infection in the study will be higher than incidence of clinical malaria resulting in adequate power.

In this study the reactogenicity (solicited local and general AEs) and the biochemistry and hematology parameters will be evaluated in a sub-cohort consisting of the first 50 subjects enrolled in each group (total 250 subjects). The anti-CS and anti-HBs immune responses will be tested in a subset consisting of the first 50 subjects enrolled in each group (total 250 subjects); see the [glossary of terms](#) for the definitions of subset and sub-cohort.

Assuming a post-vaccination anti-CS GMC of approximately 50 IU/ml for the fractional dose schedules and a log SD of 0.5 the precision obtained by 95% CIs of the GMC with a sample size of 50 subjects per group is (36.3-68.8).

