11.6. Derived and transformed data

• Immunogenicity

- A subject seropositive for anti-CS antibody will be a subject whose antibody concentration will be greater than or equal to the cut-off value (anti-CS ≥ 0.5 EU/ml).
- Seroprotection rate for anti-HBs antibody is defined as the percentage of subjects with antibody concentration greater than or equal to an established cut-off (anti-HBs ≥ 10 mIU/ml).
- The geometric mean concentration (GMC) calculations will be performed by taking the anti-log of the mean of the log transformations (base 10). Antibody concentrations below the cut-off of the assay will be given an arbitrary value of half the cut-off for the purpose of GMC calculation.

- Handling of missing data: For a given subject and a given immunogenicity measurement, missing or non-evaluable measurements will not be replaced. Therefore, an analysis will exclude subjects with missing or non-evaluable measurements.
- **Reactogenicity and safety**
 - Handling of missing data: subjects who missed reporting symptoms (solicited/unsolicited or concomitant medications) will be treated as subjects without symptoms (solicited/unsolicited or concomitant medications, respectively). In case of significant non-compliance of study procedures for reporting symptoms, the analysis plan will be reassessed to ensure more accurate reporting of study data by further analysis.
 - For the analysis of solicited symptom, missing or non-evaluable measurements will not be replaced. Therefore the analysis of the solicited symptoms based on the TVC will include only subjects/doses with documented safety data (i.e. symptom screen/sheet completed).

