- The concentration of biochemistry (ALT, creatinine) and hematology (hemoglobin, WBC, platelets) parameters in the first 50 subjects (25 subjects per site) enrolled in each group (reactogenicity sub-cohort) before Dose 3, seven days post-Dose 3 and 30 days post-Dose 3.

• Reactogenicity (reactogenicity sub-cohort)

The occurrence of solicited local and general AEs in a the first 50 subjects enrolled in each group within four days (day of vaccination and three subsequent days) after Dose 3 of study vaccine (all groups including controls), after Dose 4 (groups R012-20, R012-14, Fx012-14 and Fx017-20), after Dose 5 (groups R012-14, Fx012-14 and Fx017-20) and after Dose 6 (groups R012-14 and Fx012-14).

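### Reactogenicity percentages pooled over Doses 3 to 6 count up to four doses per child as independent, so their exact 95% CIs are likely to be too narrow in the multi-dose arms

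*SAP*

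**What the plan says.** SAP 7.5.1, following Protocol 11.10, plans two kinds of table that count doses rather than children.

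- For individual solicited events: "The percentage of doses followed by each individual solicited local and general AE will be tabulated for each dose and for the whole" period, and the sentence continues "solicited follow-up period (i.e. four days post-Dose 3, Dose 4, Dose 5 and Dose 6), with exact 95% CI". It therefore yields one row per dose and one row pooled over all solicited doses. Protocol 11.10 has the same sentence: "The percentage of doses followed by each individual solicited local and general AE will be tabulated for each dose".
- For any local, any general or any event, solicited and unsolicited combined: "The percentage of doses followed by at least one local AE (solicited and unsolicited". As a percentage of doses, this is planned only for the period as a whole.

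Both kinds are repeated for Grade 3 and vaccine-related events. On method, SAP 11.1.4.1 says "The exact CIs around within-group proportions are derived using the method of Clopper and Pearson". The same section of the SAP also plans percentages of subjects, in which each child counts once.

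**The concern.** Clopper-Pearson limits are binomial limits: they assume that every unit counted is an independent trial. In a pooled per-dose row the unit is the dose, and one child supplies up to four. If a child who reacts to one dose is more likely than others to react to the next, 200 doses from 50 children carry less information than 200 independent doses, and the interval is too short. The SAP accepts this principle elsewhere: section 7.3.1.2 models dependence between malaria episodes within a subject. Repeated doses get no such treatment.

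At stake is how precisely the sub-cohort appears to describe fractional, full and repeated doses, which is its stated purpose (Protocol section 3, safety monitoring). Within each RTS,S arm all solicited doses are of one size, so the pooled row invites use as the full-versus-fractional summary. The number of doses per child differs by arm, so intervals printed side by side under one 95% label would have different true coverage.

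**Working it through.** The documents state no event rate, interval width, coverage or within-child correlation for these rows, so there is no figure of the plan's own to reproduce.

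**Inputs from the documents**
- Children per group: 50 (Protocol 11.4: "sub-cohort consisting of the first 50 subjects enrolled in each group (total 250 subjects").
- Solicited doses (SAP 5.2): "after Dose 3 of study vaccine (all groups including controls"; Dose 4 in the four RTS,S groups; Dose 5 in R012-14, Fx012-14 and Fx017-20; Dose 6 in R012-14 and Fx012-14.
- Interval: Clopper-Pearson, two-sided 95%.

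**Assumptions**
- ICC from 0 to 0.4, rate 30% at every dose, all planned doses given, beta-binomial counts per child.

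**Step 1. Doses in the pooled row (50 × m)**
- Control: m = 1, 50 doses
- R012-20: m = 2, 100 doses
- Fx017-20: m = 3, 150 doses
- R012-14 and Fx012-14: m = 4, 200 doses each

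**Step 2. Planned interval.** With x events in n doses, the lower limit is the 2.5% quantile of Beta(x, n − x + 1) and the upper limit is the 97.5% quantile of Beta(x + 1, n − x). For x = 60 and n = 200 this gives 23.7% to 36.9%.

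**Step 3. Interval allowing for clustering.** Design effect DEFF = 1 + (m − 1) × ICC; effective n = 50m / DEFF. For m = 4 at 30%:

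| ICC | DEFF | Effective n | 95% CI |
|---|---|---|---|
| 0.1 | 1.3 | 153.8 | 22.9–37.9% |
| 0.2 | 1.6 | 125.0 | 22.1–38.8% |
| 0.3 | 1.9 | 105.3 | 21.5–39.7% |
| 0.4 | 2.2 | 90.9 | 20.8–40.5% |

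**Step 4. Actual coverage of the planned interval.** Take the beta-binomial distribution of events per child, convolve it over 50 children, and add the probabilities of all totals whose Clopper-Pearson interval contains 30%:

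| ICC | 4 doses | 3 doses | 2 doses |
|---|---|---|---|
| 0 | 95.5% | 96.0% | 96.3% |
| 0.05 | 93.8% | 95.0% | 95.8% |
| 0.1 | 92.1% | 93.9% | 95.3% |
| 0.2 | 88.7% | 91.7% | 94.2% |
| 0.3 | 85.4% | 89.5% | 93.2% |
| 0.4 | 82.3% | 87.4% | 92.1% |

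With one dose per child the ICC has no effect.

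**Step 5. Sensitivity**
- *Other rates.* Simulated over rates of 5% to 50%, 4-dose coverage is 92.2–94.1% at ICC 0.1 and 88.5–91.1% at ICC 0.2.
- *Rates that differ between doses.* With assumed rates of 10, 20, 40 and 50% (mean 30%), 4-dose coverage is about 95% at a latent within-child correlation of 0.1 and about 89% at 0.5. The shortfall is smaller than with equal rates.
- *Rare events.* At an assumed 1% rate, 4 doses and ICC 0 to 0.2, coverage stays at 95–98%.

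**The case against.** The case for leaving the plan alone is substantial.

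- *Scope.* The quoted sentence also produces one row per dose, with one dose per child, where the exact interval is valid. So are the percentages of subjects.
- *Use.* Questions about a fractional, fourth or yearly dose are answered by the single-dose rows. SAP section 8 reads these secondary endpoints descriptively, and no test or decision rule uses the pooled intervals.
- *Size.* The correlation is assumed. The solicited doses are about 12 to 18 months apart, so rates may well differ between them. Clopper-Pearson is conservative and absorbs a small correlation: at ICC 0.05, 4-dose coverage is still about 94%.
- *Remedy.* The usual cluster-robust intervals do worse for sparse events. At an assumed 1% rate, 4 doses and correlation 0 to 0.2, they covered 79–86% (Wald) or 75–82% (logit), and 13–21% of runs had no events and so no usable interval.

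All of this stands as a limit on scope and size, and the last point governs the choice of fix. None of it makes repeated doses in one child independent.

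A reader might go further and infer a downward bias in the combined tables, because under Protocol 11.6 "subjects who missed reporting symptoms (solicited/unsolicited or concomitant medications) will be treated as subjects without symptoms", while the solicited-only tables leave out doses without a record. The documents do not support that as a finding. They give no missing-record rate. Protocol 11.6 provides for reassessing the analysis plan if non-compliance is significant. Solicited events are assessed by the study physician on the vaccination day and by visiting staff on the next three days. Restricting the combined tables to doses with a solicited record would also discard unsolicited events captured separately, which is a trade-off rather than a correction.

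**Conclusion.** The interval rule is wrong as written, but only for percentages of doses pooled over the solicited period in the four RTS,S arms. Under the assumptions above (ICC 0.1 to 0.4, equal 30% rate), coverage is about 92% to 82% in R012-14 and Fx012-14, 94% to 87% in Fx017-20 and 95% to 92% in R012-20. R012-20 is barely affected at low correlation.

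Two stronger readings should be avoided. One is that the sub-cohort's reactogenicity intervals are wrong in general: single-dose rows, subject-level rows and the whole Control arm are sound. The other is that the pooled intervals are known to be too narrow: that requires positive within-child correlation, for which the documents give no value, and the loss shrinks when rates vary between doses or events are rare. No efficacy or safety conclusion in the plan depends on these intervals. The point deserves correction because the correction is easy and the printed precision would otherwise differ by arm without the reader knowing.

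**What to change.** In SAP 7.5.1, for the pooled per-dose rows only, replace the exact CI by Clopper-Pearson on the effective sample size. With K children, n doses, y_i events in m_i doses for child i, and p the pooled proportion:

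- estimate DEFF = [K/(K − 1) × Σ(y_i − m_i p)²] / [n p (1 − p)], and set it to 1 if it is smaller;
- compute Clopper-Pearson with n/DEFF doses and p × n/DEFF events;
- if no dose, or every dose, is followed by the event, use ordinary Clopper-Pearson.

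In a check by simulation (20,000 beta-binomial runs per setting, 2 to 4 doses, ICC 0.1 to 0.4), this interval covered 95–97% at rates of 10%, 30% and 50%, and 98–99% at 1%. The weakest setting was a 5% rate with 3 doses and ICC 0.4, at about 93%, against 88% for the planned interval.

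The simpler alternative is to print the pooled per-dose percentage without a CI. Either way, keep Clopper-Pearson for single-dose and subject-level rows.

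The cost is minor programming and a table footnote. The intervals become somewhat wider and usually slightly conservative: with 4 doses, by a factor of about √1.3 = 1.14 at ICC 0.1 and √2.2 = 1.48 at ICC 0.4. Point estimates do not change, and no new data are needed.
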